### 5.7.3 Handling of missing values/censoring/discontinuations

#### Censoring of RFS

If no event has occurred by the primary analysis cutoff, then RFS will be censored as the date of the last efficacy assessment (i.e. either radiological or non-radiological) prior to the analysis cutoff that shows no disease recurrence. Patient will be censored for RFS at the date of first treatment for any of the following situation:

- The censoring algorithm calls for the patient to be censored at the date of the last adequate assessment meeting a certain set of criteria (e.g. prior to subsequent anticancertherapy), but no such assessment exists.

RFS will be censored for extended loss to follow-up to account for missed efficacy assessments prior to relapse or death. Specifically, if there are two or more scheduled efficacy assessments which are missing during the first 12 months of the treatment period, two or more missing during the follow up period followed by an assessment of relapse or death (due to any cause), RFS will be censored at the last adequate assessment prior to relapse or death. If the time interval between the last adequate efficacy assessment date and the RFS event date is larger than the interval of 2 missing efficacy assessments (7 days for treatment phase and 14 days for follow-up phase, protocol-specified time window ) then the patient will be censored and the censoring reason will be 'Event documented after two or more missing tumor assessments. For this type of censoring, the 'last adequate assessment' is defined as the date of the last MRI or CT assessment prior to the missing assessments that shows no disease recurrence.

For patients who receive subsequent anti-cancer therapy the following rules will apply.

- If such therapy is started without evidence of documented disease recurrence, then RFS will be censored at the date of the last efficacy ) assessment before the date of initiation of anti-cancer therapy.
- If a patient has only a baseline visit or does not have an efficacy assessment before the date of initiation of anti-cancer therapy, RFS will be censored at the date of first treatment.

[Table 2-7](#) below further describes the algorithm to determine whether a patient should be classified as RFS event or censored.

**Table 2-7 Outcome and event/censor dates for RFS analysis**

Situation	Date	Outcome
Recurrence documented between scheduled visits	Date of assessment of Recurrence	Event

Situation	Date	Outcome
No recurrence (or death)	Date of last efficacy assessment	Censored
New anti-cancer therapy (including surgery for melanoma) started prior to documented disease recurrence*	Date of last efficacy assessment on or prior to starting anti-cancer therapy	Censored
Death before recurrence assessment	Date of death	Event
Death between adequate assessment visits	Date of death	Event
Death or recurrence after two or more missed scheduled efficacy assessments during study treatment period or after two or more missing during the follow up period	Date of last adequate assessment prior to missed assessments	Censored

\*If relapse and new anti-cancer therapy occur on the same day then the relapse will be counted as event. If anticancer therapy is started prior to any adequate assessments, censoring date should be the date of first treatment.

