Cutaneous squamous cell carcinoma (CuSCC), keratoacanthomas (KA) and new primary melanomas have been observed in patients treated with dabrafenib and dabrafenib/trametinib combination therapy. These treatment-related lesions should be surgically removed according to institutional practices. Dose modification or interruption of study treatment is not required for cuSCC, KA, or new primary melanoma. However, cuSCC and new primary melanoma should be reported as a SAE. In addition, a biopsy of the lesion should be taken, where possible, and submitted for further analyses and a summary of the results submitted to Novartis.

Subjects should be instructed to immediately inform their physician if new lesions develop. Skin examination should be performed prior to initiation of study treatment and throughout therapy as detailed in the Visit Evaluation Schedule. Monitoring should follow institutional

guidelines and/or as clinically indicated following discontinuation of dabrafenib or until initiation of another anti-neoplastic therapy.

New non-cutaneous malignancies:

In vitro experiments have demonstrated paradoxical activation of MAP-kinase signaling in *BRAF* wild-type cells with RAS mutations when exposed to *BRAF* inhibitors, which may lead to increased risk of non-cutaneous malignancies in patients treated with dabrafenib. Cases of RAS-driven malignancies have been seen with *BRAF* inhibitors, including dabrafenib. Subjects should be monitored as clinically appropriate. Consider the benefits and risks before continuing treatment with dabrafenib in subjects with a non-cutaneous malignancy harboring a RAS mutation. No dose modification of trametinib is required when taken in combination with dabrafenib.

Following discontinuation of dabrafenib, monitoring for non-cutaneous secondary/recurrent malignancies should continue for up to 6 months or until initiation of another anti-neoplastic therapy.

New cutaneous and non-cutaneous malignancies that are reported to the Investigator should be reported as an SAE. A biopsy of the new malignancy should be taken, where possible, and submitted for further analyses including RAS mutation status. Testing of these biopsies may include analysis of genomic alterations, which include but not limited to DNA, RNA and protein analysis of these biopsy specimens, and would analyze the biological pathways known to be associated with, and relevant to, *BRAF*-mutant tumor activation.

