coverage and prescribed use of contrast. The method of assessment should be noted as CT on the CRF.

Clinical examination: New lesions detected by clinical examination must be biopsied, where possible, to confirm disease recurrence. If a biopsy cannot be obtained then CT/MRI must be done to confirm disease recurrence.

CT and MRI: Contrast enhanced CT with 5mm contiguous slices is recommended. MRI is acceptable (refer to [Section 8.3.1](#)), but when used, the technical specification of the scanning sequences should be optimized for the evaluation of the type of disease.

Whenever possible the same scanner should be used.

Brain Scan: For the baseline brain scan and any post-baseline brain scans, contrast enhanced MRI is preferable to contrast enhanced CT.

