### Post treatment anti-cancer therapy

Anti-neoplastic therapies since discontinuation of study treatment will be listed and summarized by ATC class, preferred term and by means of frequency counts and percentages using FAS. Note that biopsies will not be regarded as an anti-neoplastic surgery for the purpose of this analysis.

The number and percentage of patients who reported taking at least one anti-neoplastic therapy since discontinuation of study treatment by category (e.g immunotherapy, targeted therapy, chemotherapy, radiotherapy, etc.), the duration of treatment and the best response will be summarized.

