## 5.7.1 Secondary endpoints

### Relapse free survival

RFS is defined as the time from the date of first dose of the study treatment to the date of the first documented disease recurrence or death due to any cause whichever comes first. Treatment emergent malignancies other than second melanomas will not be considered as events. The analysis will be based on FAS and will include all data observed up-to the cut-off date.

RFS will be censored if no RFS event is observed before the first to occur between: (i) the analysis cut-off date, and (ii) the date when a new anti-cancer therapy is started. The censoring date will be the date of the last adequate tumor assessment prior to data cut-off date/start of new anti-cancer therapy date (see [Section 2.7.3](#) for additional details regarding censoring rules and determination of date of last adequate tumor assessment).

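### SAP Table 2-7 has no row for second melanomas, which the RFS definition counts as events, and its surgery row would censor an excised one; the upward bias is small

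*SAP*

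**What the plan says.** SAP 5.7.1 defines RFS from first dose to first documented recurrence or death. It then adds: "Treatment emergent malignancies other than second melanomas will not be considered as events". Protocol 12.5.1 uses the same sentence. By that exception a second melanoma is an event.

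SAP 5.7.3 gives the censoring rules. For patients who go on to further anti-cancer therapy, the text reads "If such therapy is started without evidence of documented disease recurrence, then RFS will be censored at the date of the last efficacy" assessment before that therapy. Table 2-7 repeats the rule with a wider trigger: "New anti-cancer therapy (including surgery for melanoma) started prior to documented disease recurrence". The outcome is censored, and the date is given as "Date of last efficacy assessment on or prior to starting anti-cancer therapy". A footnote to that row says: "If relapse and new anti-cancer therapy occur on the same day then the relapse will be counted as event".

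Protocol 6.5.1.3.14 covers cutaneous squamous cell carcinoma, keratoacanthoma and new primary melanoma, and says: "These treatment-related lesions should be surgically removed according to institutional practices". For suspected relapse, protocol 8.3.1.1 says: "New lesions detected by clinical examination must be biopsied, where possible, to confirm disease recurrence". If no biopsy can be obtained, CT or MRI must confirm the recurrence.

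**The concern.** The definition and the classification table disagree. Table 2-7 recognises only recurrence and death as events. Surgery for melanoma counts as new therapy, and the only thing that saves a patient from censoring at that point is a recurrence already documented. A second primary melanoma is not clearly a recurrence, and surgical removal is its expected course. A programmer who works from the table would censor a patient whom section 5.7.1 calls an event, and would move the censoring date back to an assessment before the lesion was found.

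A related gap concerns relapse. A resectable relapse may first be proven on the surgical specimen. The outcome then depends on which date is recorded for the recurrence, and the SAP does not fix that date.

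At stake are the 12- and 24-month RFS rates. These are stated secondary endpoints and will naturally be read beside the COMBI-AD combination-arm rate that the protocol quotes.

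**Working it through.** **Reading the rules together, second melanoma**

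- Under SAP 5.7.1 and protocol 12.5.1 it is an event.
- Table 2-7 has no row that names it. If it is excised, the surgery row applies and the outcome is censored. If it is not excised and nothing else happens, the row for patients without recurrence or death applies, and the outcome is again censored.
- The protocol glossary uses relapse and recurrence interchangeably, for the return of disease after treatment. Protocol 10.1.2 separates malignant neoplasms from relapse of the study indication, and Table 10-1 lists new primary melanoma as its own event of special interest. On these terms a second primary is not a documented recurrence. The same-day footnote speaks of relapse, so it does not clearly reach a second primary.

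**Reading the rules together, relapse proven at resection**

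- Documented by biopsy or imaging before surgery: event.
- First proven on the specimen and dated at surgery: event, by the footnote.
- First proven on the specimen and dated at the later pathology result: surgery comes first, so censored.
- Table 2-7 gives only the date of assessment of recurrence and does not define it for histology.

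**Benchmark reproduced.** Protocol 12.7 gives a COMBI-AD combination-arm 12-month RFS of 88% (95% CI 85% to 91%). With n = 435, the standard error is √(0.88 × 0.12 / 435) = 0.0156, and 0.88 ± 1.96 × 0.0156 gives 0.849 to 0.911. This agrees with the stated interval.

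**Size for second melanomas.** Protocol 1.1.1.6 reports new primary melanoma in 1 patient of the combination group (435 patients), or 1/435 = 0.23%.

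- Events by 12 months at 88% RFS: 0.12 × 435 = 52.2.
- Share of events affected: f = 1/52.2 = 1.9%. This assumes that the one case fell within 12 months and was the patient's first RFS event.
- If a share f of events becomes censorings, the event hazard is multiplied by (1 − f), so the estimate becomes S^(1 − f) = 0.88^0.981 = 0.882, a rise of 0.2 points.
- A Kaplan-Meier check on 400,000 simulated patients, with constant hazard and censoring back-dated to the previous scheduled scan, moves from 0.8799 to 0.8819, also 0.2 points.
- At 24 months, if the hazard stays constant (an assumption), 0.88² = 0.774 becomes 0.778, a rise of 0.4 points.
- In this trial's 556 patients the same rate implies 556 × 1/435 = 1.3 patients.

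For scale, the 95% half-width at 88% with 556 patients is 1.96 × √(0.88 × 0.12 / 556) = 2.7 points.

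**Size for relapses.** The documents give no share of relapses first proven on a specimen and dated after surgery. With dating at surgery the effect is zero. Purely as assumed shares, the same simulation gives rises at 12 months of about 0.5 points if 5% of RFS events are affected, 1.1 if 10%, 2.8 if 25% and 5.7 if 50%. Nothing in the documents selects among these.

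**The case against.** **The table only elaborates the definition.** SAP 5.7.1 censors only when no RFS event has been observed before new therapy, and 5.7.3 introduces Table 2-7 as further description. A second melanoma biopsied before removal is, on that reading, already an observed event. This is a fair way to read 5.7.1, but it does not remove the conflict. The table still tests for recurrence alone. Protocol 6.5.1.3.14 asks for a biopsy where possible, but for further analyses; it does not say that the diagnosis must precede excision.

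**Relapses are not simply lost.** A reader might infer that every relapse first proven on a specimen is censored and that RFS is overstated by several points. The documents do not support that. The footnote covers such a relapse if it is dated at surgery. Protocol 8.3.1.1 pushes biopsy or imaging ahead of surgery, and Table 2-7 makes recurrence documented between visits an event. The larger figures above rest on assumed shares. This objection stands: for relapse the defect is an undefined date. One supporting argument is weaker than it looks. The statement "Note that biopsies will not be regarded as an anti-neoplastic surgery for the purpose of this analysis" belongs to the summary of post-treatment therapy in SAP 5.4.2 and is not carried into the RFS rules.

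**The surgery row has a legitimate use.** Inclusion criterion 3d does not require complete nodal resection for microscopic disease. A later completion dissection could find residual nodal disease without a relapse. This also stands, so the row should be narrowed and not deleted.

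**RFS carries no test.** SAP 5.7.2 analyses it descriptively, and the interim futility look had its own SAP and is complete. This limits the consequence, but a descriptive rate still needs an event rule that matches its definition.

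**Conclusion.** The plan is wrong as written, with a small effect. For second melanomas, Table 2-7 contradicts the RFS definition in the same SAP and in the protocol. For relapses proven on a resection specimen, the SAP leaves open a date that decides between event and censoring. Both faults can only push RFS upward.

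The one size anchored in the documents is about 0.2 points at 12 months. It rests on a single COMBI-AD case, on that case falling within 12 months, and on the table being followed literally. For relapses the amount is unknown, and zero if they are dated at surgery. The primary endpoint, its success criterion and every formal decision are unaffected.

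**What to change.** In SAP 5.7.3 and Table 2-7:

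1. Add a row: second (new primary) melanoma; date of diagnosis (biopsy or excision); event.
2. State that recurrence proven on a biopsy or surgical specimen is dated at that procedure, so that the same-day footnote applies.
3. Limit the surgery censoring row to surgery that does not yield recurrent or second melanoma, and state how a completion node dissection is handled.

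The cost is minor SAP wording and RFS programming, and a slightly lower reported RFS. The programming should name its source for specimen histology. The protocol collects anti-neoplastic surgery and asks for new primary melanomas to be reported as serious adverse events, but it does not describe a dedicated field for the histology of an excision. No clinical procedure changes.

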## Censoring of OS

If a patient is not known to have died at the time of analysis cut-off, then OS will be censored at the date of last known date when patient was alive, i.e., last contact date.

## 5.8 Safety analyses

All safety analyses will be based on safety set.

### 5.8.1 Adverse events (AEs)

Adverse events are coded using MedDRA terminology. The MedDRA 24.1 version used for reporting will be specified in the CSR and as a footnote in the applicable tables/listings. AEs will be assessed according to the Common Terminology Criteria for Adverse Events (CTCAE) version 4.03.

AE summaries will include all AEs occurring during on-treatment period. All AEs collected in the AE (e)CRF page will be listed along with the information collected on those AEs e.g. AE relationship to study drug, AE outcome etc. AEs with start date outside of on-treatment period will be flagged in the listings.

AEs will be summarized by number and percentage of subjects having at least one AE, having at least one AE in each primary system organ class (SOC) and for each preferred term (PT) using MedDRA coding. A patient with multiple occurrences of an AE will be counted only

once in the respective AE category. A subject with multiple CTCAE grades for the same preferred term will be summarized under the maximum CTCAE grade recorded for the event.

AE with missing CTCAE grade will be included in the 'All grades' column of the summary tables.

In AE summaries, the primary SOC will be presented alphabetically and the preferred terms will be sorted within primary SOC in descending frequency. The sort order for the preferred term will be based on their frequency.

The following adverse event summaries will be produced: overview of adverse events and deaths, AEs by PT, SOC and PT, summarized by relationship to study treatment, seriousness, leading to treatment discontinuation, leading to dose interruption/adjustment, requiring additional therapy and leading to fatal outcome. In addition, a summary of serious adverse events with number of occurrences will be produced (an occurrence is defined as >1 day between start and prior end date of record of same preferred term). Note that Adverse events leading to fatal outcomes with relationship is a EudraCT requirement.

The proportion of subjects in the study, who have permanently discontinued treatment due to any AE PT, will be estimated along with 95% confidence intervals using Clopper Pearson exact method.

### 5.8.1.1 Pyrexia

For pyrexia, other characteristics like number of episodes, duration, and AE management (including concomitant medications and study treatment modifications) due to pyrexia will be summarized..

The number (%) of patients who received medications for treatment of pyrexia will be summarized along with the type of medications.

### 5.8.1.2 Adverse events of special interest (AESI)/grouping of AEs

All AESI definitions or AE grouping for the clinical program need to be specified in the Compound Case Retrieval Strategy sheet (CRS) with one exception of pyrexia AESI with clear versioning and reference to the MedDRA version used. The CRS version will be included in a footnote of the AESI tables.

Pyrexia AESIs will be defined using the following list of PTs:

Pyrexia PT	PT Code
Body temperature increased	10005911
Cytokine release syndrome	10052015
Hyperpyrexia	10020741
Hyperthermia	10020843
Influenza like illness	10022004
Pyrexia	10037660
Sweating fever	10042666
Systemic inflammatory response syndrome	10051379
Tumour associated fever	10052243

**Table 2-6 Adverse events of special interest by study treatment**

	trametinib	dabrafenib	dabrafenib and trametinib combination
Hepatic disorders	x		x
Pneumonitis/Interstitial lung disease	x		x
Skin toxicities (e.g., rash, dermatitis acneiform)	x		x
Bleeding events	x		x
Hypersensitivity	x	x	x
Pancreatitis		x	x
Neutropenia			x
Pulmonary embolism, deep vein thrombosis	x		x
Pre-renal and intrinsic renal failure		x	x
New primary melanoma		x	x
Non-Cutaneous Treatment-Emergent Malignancies		x	x
Hyperglycemia		x	x
Cardiac related events	x		x
Complicated pyrexia and/or Grade 3 and Grade 4 pyrexia		x	x
Uveitis		x	x
Ocular events (e.g., retinal vein occlusion, retinal pigment epithelial detachment and uveitis)	x		x
Cutaneous squamous cell carcinoma including keratocanthoma		x	x
Hypertension	x		x

### Data analysis of AESIs

An adverse event of special interest is a grouping of adverse events that are of scientific and medical concern specific to each components of study treatment, i.e. dabrafenib and trametinib. These groupings are defined using MedDRA terms, SMQs (standardized MedDRA queries), HGLTs (high level group terms), HLT (high level terms) and PTs (preferred terms). Customized SMQs (Novartis MedDRA queries, NMQ) may also be used. A NMQ is a customized group of search terms which defines a medical concept for which there is no official SMQ available or the available SMQ does not completely fit the need. It may include a combination of single terms and/or an existing SMQ, narrow or broad. For each specified AESI, number and percentage of patients with at least one event of the AESI occurring during on treatment period will be summarized.

A listing of all grouping levels down to the MedDRA preferred terms used to define each AESI will be generated.

Summaries of these AESIs will be provided, (specifying PTs, grade, serious adverse event (SAE), relationship, leading to treatment discontinuation, leading to dose adjustment/interruption, hospitalization, death etc.).

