If early treatment discontinuation occurs due to reason other than disease relapse or a subject has completed treatment and has not relapsed, refer to [Table 8-2](#).

Table 8-2 Follow-up (Pre-Relapse) Assessment Schedule

	Pre-Relapse Visit & Assessment Schedule ¹							
Visit Name	Month 3	Month 6	Month 12	Month 15	Month 18	Month 24	Survival Contact (every 3 mo) ²	End of Study (EoS) ³
Physical Examination	X	X	X	X	X	X		X ³
ECOG Performance Status	X	X	X	X	X	X		X ³
Chest, abdomen and pelvic CT scans ⁴	X	X	X	X	X	X		X ³
Dermatologic Assessment	X	X	X	X	X	X		X ³
Patient reported outcomes	X	X	X	X	X	X		X ³
Any anti-neoplastic therapy (including surgery, radiotherapy, medications) since discontinuation of study treatment including Best Response	X	X	X	X	X	X	X	X
Survival Follow Up	X	X	X	X	X	X	X	X
Disposition Assessment (at the end of each study period)								X

¹ Follow-up will start once treatment is completed or discontinued and should continue through EoS Visit, withdrawal or death, even if disease recurs. Follow-up visits prior to disease recurrence should follow [Table 8-2](#), and should be clinic visits through the Month 24 Assessment. Follow-up visits after the Month 24 Assessment are not required to be clinic visits and the information collected will be limited to the following: any radiotherapy; surgical procedure or new anti-cancer therapy initiated until EoS visit, withdrawal or death; best response to any follow-up treatment; and survival data. For example, if a subject discontinues treatment at Month 2 for reason other than disease relapse, the EoS should be performed according to [Table 8-1](#) and the follow-up assessments would start at Month 3 according to [Table 8-2](#) until EoS, withdrawal or death. Follow-up after disease relapse should follow the schedule in [Table 8-3](#).

² Survival follow-up after the Month 24 assessment should be conducted every 3 months until withdrawal, death, or study end (whichever occurs first), and can be done via phone contact.

³The EoS visit should be completed at withdrawal, lost to follow-up, death, or at the end of study (see definition in [Section 9.2](#)), whichever occurs first. If the EoS visit occurs after the Month 24 visit, a clinic visit is not required and the information collected will be limited to the following: anti-cancer therapy, best response to any follow-up treatment, and survival data

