9.1 Discontinuation

9.1.1 Discontinuation of study treatment

Discontinuation of study treatment for a subject occurs when study treatment is stopped earlier than the protocol planned duration, and can be initiated by either the subject or the investigator.

The investigator must discontinue study treatment for a given subject if, he/she believes that continuation would negatively impact the subject's well-being.

Study treatment must be discontinued under the following circumstances:

- Disease relapse
- Unacceptable adverse event, including meeting stopping criteria as described in [Sections 6.5.1](#) and [6.5.2](#).
- Subject/guardian decision
- Pregnancy
- Use of prohibited treatment as per recommendations in [Section 6.2.2](#)
- Any situation in which study participation might result in a safety risk to the subject.

If discontinuation of study treatment occurs, the investigator should make a reasonable effort to understand the primary reason for the subject's premature discontinuation of study treatment and record this information.

Subjects who discontinue study treatment or who decide they do not wish to participate in the study further should NOT be considered withdrawn from the study UNLESS they withdraw their consent (see [Section 9.1.2](#)). **Where possible, they should return for the assessments indicated** in the assessment schedule. If they fail to return for these assessments for unknown reasons, every effort (e.g. telephone, e-mail, letter) should be made to contact the subject/pre-designated contact as specified in the lost to follow-up section (see [Section 9.1.3](#)). This contact should preferably be done according to the study visit schedule.

If the subject cannot or is unwilling to attend any visit(s), the site staff should maintain regular telephone contact with the subject, or with a person pre-designated by the subject. This telephone contact should preferably be done according to the study visit schedule.

After study treatment discontinuation, at a minimum, in abbreviated visits, the following data should be collected at clinic visits or via telephone/email contact (per assessment schedule in [Table 8-2](#) or [Table 8-3](#)):

- new / concomitant treatments including any radiotherapy, surgical procedure or new anti-cancer therapy
- adverse events/Serious Adverse Events
- survival status

The investigator must also contact the IRT to register the subject's discontinuation from study treatment.

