10.1.3 SAE reporting

To ensure subject safety, every SAE, regardless of suspected causality, occurring after the subject has provided informed consent and until at least 30 days after the subject has stopped study treatment must be reported to Novartis within 24 hours of learning of its occurrence. Detailed instructions regarding the submission process and requirements are to be found in the investigator folder provided to each site.

Any additional information for the SAE including complications, progression of the initial SAE, and recurrent episodes must be reported as follow-up to the original episode within 24 hours of the investigator receiving the follow-up information. An SAE occurring at a different time interval or otherwise considered completely unrelated to a previously reported one must be reported separately as a new event.

Any SAEs experienced after the 30 day safety evaluation follow-up period (or 5 half-lives, whichever is longer) must only be reported to Novartis if the investigator suspects a causal relationship to the study treatment.

Information about all SAEs is collected and recorded on the Serious Adverse Event Report Form; all applicable sections of the form must be completed in order to provide a clinically

thorough report. The investigator must assess and record the relationship of each SAE to each specific study treatment (if there is more than one study treatment). Instructions regarding the SAE submission process and requirements for signatures are to be found in the investigator folder provided to each site.

Follow-up information is submitted in the same way as the original SAE Report. Each re-occurrence, complication, or progression of the original event must be reported as a follow-up to that event regardless of when it occurs. The follow-up information must describe whether the event has resolved or continues, if and how it was treated, whether the blind was broken or not, and whether the subject continued or withdrew from study participation.

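### Non-cutaneous malignancies found between day 31 and month 6 after treatment fall inside the protocol's monitoring period but enter no planned AESI rate, and the rules for reporting them conflict

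*SAP*

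**What the plan says.** **Monitoring and reporting (protocol 6.5.1.3.14).** For non-cutaneous disease: "Following discontinuation of dabrafenib, monitoring for non-cutaneous secondary/recurrent malignancies should continue for up to 6 months or until initiation of another anti-neoplastic therapy". For cutaneous disease no fixed period is set; monitoring follows institutional "guidelines and/or as clinically indicated following discontinuation of dabrafenib or until initiation of another anti-neoplastic therapy". On reporting: "New cutaneous and non-cutaneous malignancies that are reported to the Investigator should be reported as an SAE". No end date is attached to that instruction.

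**General SAE rule (protocol 10.1.3).** SAEs arising after 30 days (or 5 half-lives, if longer) "must only be reported to Novartis if the investigator suspects a causal relationship to the study treatment".

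**Collection after stopping (protocol 9.1.1).** The minimum data after treatment discontinuation include "adverse events/Serious Adverse Events", to be gathered on the schedule of Tables 8-2 and 8-3. Neither Table 8-2, the "Follow-up (Pre-Relapse) Assessment Schedule", nor its post-relapse counterpart has a row for adverse events.

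**Analysis (SAP 5.1.1 and 5.8.1.2; protocol 12.5.2).** The on-treatment period ends 30 days after the last dose of either drug. Safety tables use on-treatment data, and for each AESI the "number and percentage of patients with at least one event of the AESI occurring during on treatment period will be summarized". Post-treatment safety data are listed and flagged. Non-cutaneous treatment-emergent malignancies, cutaneous squamous cell carcinoma and new primary melanoma are all named AESIs.

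**The concern.** The protocol gives a mechanism for this risk (paradoxical MAP-kinase activation and RAS-driven tumours with BRAF inhibitors) and for that reason asks sites to keep looking after the drug is stopped. The planned rate stops counting at day 30, well before the looking stops. Whether a later case even reaches the database may depend on which passage a site follows. A reader of the study report would see a malignancy rate that covers only the first part of the period in which the protocol wanted such events sought. Most of these patients are disease-free after surgery, so even a small rate of second cancers matters to the benefit-risk reading.

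**Working it through.** The plan states no figure here to reproduce. The check compares time windows and traces one case through the rules.

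**1. Does the half-life clause lengthen the 30 days?** Half-lives from protocol 1.1.1.1: trametinib 127 h, dabrafenib 8 h.
- Trametinib: 5 × 127 / 24 = 26.5 days.
- Dabrafenib: 5 × 8 / 24 = 1.7 days.

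Both are under 30 days, so the cut-off stays at 30.

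**2. How much of the monitoring period is uncounted?** A month is 28 days in protocol section 3 and 30.4375 days in SAP 5.1.1. Assume both drugs stop together and no new anti-neoplastic therapy starts.
- 28-day months: 6 × 28 = 168 days; 168 − 30 = 138 uncounted (138/168 = 82%).
- 30.4375-day months: 6 × 30.4375 = 182.6 days; 182.6 − 30 = 152.6 uncounted (84%).

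These are shares of calendar time after the last dose, not of events. Measured from first dose to 6 months after a full 12-month course, the uncounted part is 138/504 = 27% or 152.6/547.9 = 28%.

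**3. Which scheduled examinations fall where, for a completer?** Take the last dose as day 336, so the counted window closes at day 366. Visit day = 28k + 1 (SAP 5.1.1); visit windows are from protocol 8.3.1.1.
- Month 12 CT and skin examination: day 337 ± 7, i.e. days 330–344, inside the counted window.
- Month 15: day 421 ± 14, i.e. days 407–435, which is 71–99 days after the last dose. Outside the counted window, inside the monitoring period.
- Month 18: day 505, 169 days after the last dose, at about the end of the monitoring period.

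**4. What happens to a non-cutaneous malignancy found at Month 15?**

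| Rule | Consequence |
|---|---|
| Protocol 6.5.1.3.14 | Within the monitoring period; report as SAE |
| Protocol 10.1.3 | Reported only if causality is suspected |
| Protocol 9.1.1 | AE/SAE collected, but on schedules with no AE row |
| SAP 5.8.1.2 | Not in the AESI rate |
| SAP 5.7.1 (RFS) | Not an event; only second melanomas are excepted |
| SAP 5.1.1 | Listed and flagged, if recorded |
| SAP 5.8.2 | In the all-deaths summary, if fatal |

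Protocol 9.1.1 defines discontinuation as stopping earlier than planned, while the glossary defines it as stopping permanently for any reason. Whether 9.1.1 covers subjects who complete 12 months is therefore unclear.

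**5. Illustrative size.** COMBI-AD had 5 non-cutaneous malignancies in 435 treated patients (protocol 1.1.1.6). The documents do not give the observation window B for that count, so B is varied from 12 months + 30 days to 24 months. Assume a constant hazard h = −ln(1 − 5/435)/B and 556 subjects all treated for 12 months.
- B = 366 days: counted 556 × (1 − e^(−366h)) = 6.4; to 6 months 556 × (1 − e^(−504h)) = 8.8; difference 2.4.
- B = 672 days: counted 3.5; to 6 months 4.8; difference 1.3.
- With 30.4375-day months the differences run from 1.3 to 2.5.

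**The case against.** The strongest reply is that the plan is consistent and its label honest. Protocol 12.5.2 sets the same on-treatment period, treatment-emergent is defined by it, and the AESI in question carries that term in its name. The SAP does not depart from the protocol, and a longer window answers an additional question. All of this stands. It does not explain why a risk that the protocol follows for up to 6 months is summarised for only 30 days. SAP 5.8.2 already goes beyond the on-treatment period for deaths.

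A second reply is that late events are not lost. Protocol 9.1.1 calls for AE/SAE collection after stopping, 6.5.1.3.14 has its own open-ended SAE instruction, 10.1.2 treats non-relapse malignancies as serious, and 10.1.3 still admits cases with suspected causality. Table 8-2 keeps CT and skin examinations to Month 24 before relapse. With counts this low, a listing shows every recorded case. This too largely stands. A reader might infer that collection is cut off at day 30; the documents show conflicting instructions, not an absence of them. But a listing supplies no rate, and it cannot show a case that a site did not report because it followed 10.1.3.

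Third, 138 to 153 days is a span of time, and the expected number of cases is small. In a single-arm study some added cases would be background: COMBI-AD placebo had 3 non-cutaneous malignancies. That is correct and limits what a longer-window rate can show.

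**Conclusion.** The mismatch is real but narrow. A non-cutaneous malignancy arising in the last 138 to 153 days of a 168- to 183-day monitoring period enters no planned AESI rate, and the passages on reporting it disagree. The day counts assume that both drugs stop together and that no new anti-neoplastic therapy ends monitoring early. The figure of 1.3 to 2.5 cases outside a counted 3.5 to 6.4 rests on a constant hazard and an assumed COMBI-AD window, and should be read only as an order of magnitude.

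Three wider readings are not supported:
- A reader might infer that the 6-month period also covers cutaneous squamous cell carcinoma and new primary melanoma. Protocol 6.5.1.3.14 gives no fixed period for cutaneous disease, and second melanomas can count as RFS events after day 30.
- A reader might infer that no scheduled examination falls in a completer's counted window. The Month 12 CT and skin examination do.
- A reader might call the on-treatment rate wrong. It is correct for its stated window; the lack is of a companion figure for the longer one.

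The primary pyrexia endpoint and the decision rules are unaffected. The change is worth making because it is cheap.

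**What to change.** **SAP 5.8.1.2.** Beside the on-treatment AESI table, add a supplementary summary of malignancy AESIs that includes post-treatment events. For non-cutaneous malignancies, run it to at least 6 months after the last dabrafenib dose or the start of new anti-neoplastic therapy. State the month length used. Late cutaneous squamous cell carcinoma and new primary melanoma may be shown as recorded, without implying a prescribed 6-month window. Person-time or a time-to-event estimate would help with unequal follow-up. Add a short statement of how completely events after day 30 were collected, separately for early stoppers and completers.

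**Protocol.** Sections 6.5.1.3.14, 9.1.1 and 10.1.3 and Tables 8-2 and 8-3 must be reconciled on the reporting of new malignancies after day 30, including whether subjects who complete treatment are covered.

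**Cost.** One extra table, a sentence on completeness, and a clarification of reporting. The Month 15 and Month 18 visits with their CT and skin examinations already exist. The SAP's last revision is dated before final database lock, so the analysis change was feasible then. The reported rate may become slightly less favourable and, with no control arm, will include some background cases; the table should say so.
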